4. ESTIMATED DURATION OF THE STUDY

Study enrollment will occur over approximately a two year period. Completion of the entire protocol, including subject recruitment, study procedure execution, and statistical analysis is anticipated to take no longer than four years.

Each subject will be enrolled for a 7 week period, including a screening phase. Study procedures involve weekly clinic visits as an outpatient. Approximately 72 patients will be randomly assigned to either 84 IU of oxytocin (equivalent to 42 IU BID), 168 IU of oxytocin (84 IU BID) or vehicle placebo. The doses of oxytocin are based upon previous studies in humans showing improvement in schizophrenia related changes in behavior and brain function (Kosfeld et al, 2005; Kirsch 2005; Heinrich M 2003).

The total study duration for each individual subject will be approximately 7 weeks, which includes a 7-day screening period, a baseline (randomization) visit, and the six-week treatment phase.

Participants will remain on their current antipsychotic medication and dose throughout the study.

5. LAY LANGUAGE SUMMARY OR SYNOPSIS (no more than one paragraph)

The purpose of this study is to test whether or not people with schizophrenia feel improvement in their symptoms when oxytocin nasal spray is added to their current medications. Volunteers will be randomly assigned to one of three groups; a higher dose group, a lower dose group, or a group who receives a nasal spray with no medication in it (placebo). Volunteers will be asked questions about their mental and physical health as well as take several computer tests to track any changes over the 7 weeks of the study.

6. SPECIFIC AIMS

The proposed study is a randomized, double-blind, placebo-controlled dose-ranging, pilot study intended to replicate and extend the promising results from an earlier proof of concept study testing intranasal oxytocin in schizophrenia. This second-stage pilot study will seek to obtain information not obtained in the limited proof-of-concept study; specifically, the optimal dose of oxytocin for efficacy and tolerability, the time to optimal efficacy and the effects of longer term exposure (6 weeks) to daily intranasal oxytocin. It is expected that the information obtained from this pilot study will provide indispensable information for the design and execution of future full scale parallel arm studies to test the efficacy and safety of intransal oxytocin. It may also provide valuable information for other pilot studies that may test oxytocin in other clinical populations, and ultimately for the development of new treatment strategies for psychosis and other mental disorders based upon the use of oxytocin or oxytocin analogs.

Specific Aim #1:To replicate the promising positive findings from the pilot study in a larger and more diverse sample of subjects recruited from more than one site. In the recent pilot-study mentioned, 80 IU of intranasal oxytocin significantly improved positive and negative symptoms of schizophrenia and short term memory recall. However that study was conducted in a small number of subjects using a crossover experimental design. These findings are very promising but need to be replicated with a larger number of subjects representing more than one recruitment site.

Specific Aim #2: To investigate the efficacy and safety of higher doses of oxytocin. The original study used 80 IU of intranasal oxytocin and this was found to be well tolerated and effective. However the effect size in this study was moderate. It is possible that higher doses of oxytocin would produce stronger therapeutic effects; therefore, this study proposes to test a higher dose of oxytocin, 168 IU, in addition to the approximate dose tested in the pilot study.

Specific Aim #3:Establish the time needed to reach peak efficacy. Duration of treatment in the original study was three weeks, and significant therapeutic benefit was observed only at the three-week endpoint but not earlier. In the proposed study, subjects will receive study drug for 6 weeks and we expect that the size of the therapeutic benefit of oxytocin will increase from 3 to 6 weeks.

Specific Aim # 4: Investigate the possible cognitive effects of intranasal oxytocin. In the pilot study, oxytocin significantly improved short term recall performance in the California Verbal Learning Test. This raises the possibility that chronic oxytocin will improve cognitive deficits associated with schizophrenia. This study will test this hypothesis using the Computerized Multiphasic Interactive Neurocognitive DualDisplay™ System (CMINDS®) and Mayer-Salovey-Caruso Emotional Intelligence Test: Managing Emotions (MSCEIT™ ME).

Specific Aim #5: To determine if daily intranasal oxytocin is sufficiently safe, feasible and acceptable to patients to warrant further clinical development. Information derived from this study will inform development of oxytocin not only for schizophrenia but other potential neuropsychiatric disorders.

Specific Aim #6: The objective of the study is to compare the efficacy of intranasal oxytocin versus intranasal placebo to improve symptoms in schizophrenia patients who have residual symptoms despite being on adequate treatment with antipsychotic medication. Improvement will be measured by total score in the Positive and Negative Syndrome Scale (PANSS).

Specific Aim #7: To determine if oxytocin-induced enhancement of mu-rhythm suppression of 'mirror' neurons in schizophrenia patients can serve as a predictive biomarker of individual clinical response to this neurohormone.

Secondary objectives include:

 To evaluate the efficacy of intranasal Oxytocin as measured by change in the total CGI-Severity and Improvement scores

- To evaluate the efficacy of intranasal Oxytocin as measured by change in the total GAF score
- To evaluate the efficacy of intranasal Oxytocin as measured by change in the total scores of HAM-A.
- To evaluate the efficacy of intranasal Oxytocin on self-rated social anxiety as measured by change in the total Social Phobia Inventory (SPIN).
- To evaluate the efficacy of intranasal Oxytocin as measured by change in the total Calgary Depression Scale for Schizophrenia (CDSS) scores.
- To evaluate the safety of intranasal Oxytocin as measured by reported Adverse Events
- To evaluate the safety of intranasal Oxytocin as measured by collected safety measures to include blood tests, witnessed and reported adverse events
- To evaluate changes in ability to infer the mental state of others from emotion differentiation by their performance with the Penn Emotion Recognition Test (ER-40).
- To evaluate the possible correlation between the response to intranasal Oxytocin and biological markers, specifically endogenous oxytocin levels (tested via blood and saliva sample). Using saliva to test hormone levels has become a preferred method. Many hormone levels can fluctuate throughout the day. Using saliva allows for convenient specimen collection at multiple times (ie, pre and post dose). There is a believed correlation between the "bioavailable" (or active) amount of hormone in the blood and the levels found in saliva. We will collect both blood and saliva samples to confirm or reject the proposed correlation which may lead to a more convenient way of collection in future trials. Determining hormone bioavailability is critical with hormones and saliva as the specimen medium is ideal for this.
- To assess the differential effect of oxytocin on early environment and social parameters based on scores on the Childhood Trauma Questionnaire (CTQ) and Experience Close Relationships (ECR).
- To detect and monitor any changes in sexual functioning as rated by the Arizona Sexual Experience Scale (ASEX)
- To determine if expected deficits in neural processing of socially relevant visual stimuli (mu-rhythm suppression of mirror neurons) in schizophrenia patients correlates with the severity or nature of their symptoms
- To determine if intranasal oxytocin can improve mu rhythm suppression in schizophrenia patients

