thought to index the activity of 'mirror' neurons. Mu rhythms, measured from this brain region show reliable, dose dependent, suppression when the subject perceives biological motion (but not non-biological motion). Thus, mu wave suppression is an easily quantifiable operational measure of the neural processing of biological motion. In a recently published study conducted in [name] laboratory, the applicant showed that neural mu wave suppression induced by biological motion is impaired in first-episode of psychosis subjects, and that the neural impairment is inversely correlated with negative symptoms and social adjustment, providing construct validity for the mu suppression paradigm as an operational measure of social cognition in patients with psychosis (Singh, et,al, 2010).

Given OT's strong implication in social perception, it would be reasonable to expect that exogenous OT affects mu wave suppression in the context of biological motion. This has been in fact, confirmed in a recent study by Keri et al. using a well-established paradigm of biological motion similar to that used by our group. Keri et al, demonstrated that intranasal OT significantly enhanced detection of biological motion (human form) but not non-biological motion (rotating circle) compared to intranasal placebo. Taken together, the applicant's study and that by Keri et al, demonstrate that patients with psychosis have impaired biological motion induced mu suppression compared to normal subjects and that intranasal OT enhances this neural process in normal subjects. It is reasonable to expect that intranasal oxytocin will improve mu suppression in schizophrenia patients and we expect to demonstrate this. We also expect to find that subjects with the greatest enhancement in mu suppression are more likely to experience clinical improvement in response to 6-weeks of oxytocin treatment.

Hypothesis: We hypothesize that augmentation of antipsychotics with intranasal oxytocin will significantly improve psychopathology ratings as compared to placebo and an improvement in certain cognitive functions may be also observed.

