- Complete a questionnaire about symptoms of paranoia and sexual functioning
- Complete a test onability to recognize emotions called the Penn Emotion Recognition Test (ER-40).

Additionally at Visit 8 (week 6 or Early Termination);

- Complete a series of activities which will be used to measure process of thought called the CMINDS® and MSCEIT™ ME
- Have an additional blood sample taken (about 1 tablespoon) to monitor study drug levels in the blood
- EEG paradigm will be conducted

Follow Up Call

The volunteer will be asked to contact the study site one week after the last study drug dose to report taking any new medications or any unusual experiences since stopping the study drug.

Administration and dispensing of the study medication:

Except the one time challenge dose, this is a double-blind study, participants will be randomized to receive one of three possible intranasal study medications adjunctive to their antipsychotics: oxytocin 84 IU, oxytocin 168 IU or placebo (vehicle without oxytocin). Randomization will be performed stratifying gender groups, type of antipsychotic (typical versus atypical) and severity of symptoms based upon PANSS score (<90 versus >90) so that gender, symptom severity and antipsychotic type are distributed relatively evenly across treatment groups. Bottles containing placebo or two different concentrations of oxytocin will be formulated (See Study Drug Formulation below) so that the concentration of oxytocin in the high dose (168 IU) will be double that of the low dose (84 IU). All subjects will be instructed to spray 7 pumps of the spray bottle (one in each nostril, alternating nostrils) to achieve correct dose in the morning and again in the afternoon. Subjects will be given enough study drug at the time of the visit to last until the next visit with extra to cover approximately three additional days. Each pump bottle has 5 ml (300 IU) which is enough for 2.5 days of study drug. Therefore, subjects will be given one spray bottle supply at the time of each visit. The weight of each bottle will be recorded prior to dispensing. After all procedures are performed on baseline visit and study drug is randomly assigned, a dose of the study drug will be taken at the study site, in the presence of a staff member to insure correct administration.

Study Drug Compliance

- 1. Subjects will be instructed on proper use of the nasal device from study staff.

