PANSS scores, duration of illness, class of medication) will be tested using treatment-by-baseline characteristic interaction terms in the MMRM LDA and/or ANCOVA models. To assess impact of improvement in one domain (e.g. positive symptoms) on the efficacy of a related symptom domain (e.g. negative symptoms), a mediator analysis model with terms for treatment, baseline, and positive symptoms improvement will be applied to determine significance of oxytocin effect on reductions in negative symptoms after adjustment for potential positive symptom improvement. We will perform similar mediator analysis for assessing inter-relationships between cognitive improvement and symptom improvement in positive and/or negative symptoms. In addition, cross-sectional baseline and longitudinal change score associations between treatment outcome measures and mediator effects will be assessed by including mediators as time-varying covariates in the MMRM LDA models (Diggle et al., 2001).

MU-Suppression. Data will be analyzed in two ways. Pearson rank correlations will be used to examine correlations between mu wave suppression in response to a single dose of OT and symptom severity at the end of 6 weeks of treatment. In additional exploratory analyses, mu suppression values will be split at the median into High suppressors and Low suppressors and followed up by correlations with symptom measures to determine if initial high suppression is correlated with greater improvement in symptom severity. Secondarily, Pearson rank correlations will be conducted between mu wave suppression and symptom severity at baseline, and between mu wave suppression and symptom severity after administration of a single dose of oxytocin.

Safety Endpoints. The safety dataset will contain all subjects who take at least one dose of oxytocin. All adverse events will be coded using the most current version of the Medical Dictionary for Regulatory Activities (MedDRA). The number and percentage of subjects reporting treatment-emergent adverse events will be tabulated within each dose group by treatment, system organ class (SOC) and MedDRA-preferred term. Treatment-emergent adverse events will be those adverse events that begin or worsened following the first dose of study drug. Adverse events will be further classified by severity and investigator-assigned relationship to study drug.

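### The objective of testing whether oxytocin improves mu suppression has no analysis that estimates a drug effect, and the EEG recorded at Visit 8 under randomised treatment is left unused

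*Combined protocol and SAP*

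**What the plan says.** Section 6 contains three separate mu-suppression questions. Specific Aim 7 asks whether the oxytocin-induced enhancement "can serve as a predictive biomarker of individual clinical response to this neurohormone". One secondary objective asks whether mu deficits correlate with symptoms. Another is "To determine if intranasal oxytocin can improve mu rhythm suppression in schizophrenia patients". On this last one, section 7 says: "It is reasonable to expect that intranasal oxytocin will improve mu suppression in schizophrenia patients and we expect to demonstrate this".

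The schedule in section 9 shows EEG twice at screening and once at Visit 8/ET. The two screening recordings lie either side of a single oxytocin dose that every subject receives before randomisation and outside the blind. For Visit 8 the procedures say "EEG paradigm will be conducted". EEG participation is an optional sub-study of unstated size.

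The analysis text for mu suppression opens with "Data will be analyzed in two ways". First, with symptoms taken at week 6, "Pearson rank correlations will be used to examine correlations between mu wave suppression in response to a single dose of OT and symptom severity". Second, values are "split at the median into High suppressors and Low suppressors and followed up by correlations with symptom measures". Further correlations with symptoms are planned at baseline and after the single dose. The Analysis Methods paragraph lists the secondary measures for the mixed model; mu suppression is not among them.

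**The concern.** A correlation between mu suppression and symptoms tells us whether the two vary together across patients. It does not tell us whether oxytocin changed mu suppression. Correlations suit Aim 7 and the symptom-correlation objective, but the objective about improvement is left without an estimator.

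At stake is a stated secondary objective that the authors expect to demonstrate. With no analysis fixed in advance, it will go unanswered, or it will be answered afterwards with a comparison chosen when the data are in hand. Five recording sites and several video conditions leave ample room for choice. The ready-made contrast, before against after the challenge, has no control group. The one EEG recording made under randomised treatment has no planned use.

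**Working it through.** **Each mu question against the planned analyses**

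| Question (section 6) | Quantity needed | Planned in section 9? |
|---|---|---|
| Aim 7: prediction of response | Association of single-dose mu response with outcome | Yes: correlation, median split |
| Mu deficit and symptoms | Cross-sectional association | Yes: baseline correlation |
| Does oxytocin improve mu suppression? | Difference in mu suppression, oxytocin minus placebo | No |

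No listed mu analysis has a treatment-arm term or uses a Visit 8 mu value. The only between-group EEG statement, in the mu paradigm description, concerns occipital power. It is a check on posterior alpha, with no arms, visit or test defined, and it does not compare central mu suppression by arm.

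**What the unused comparison could deliver**

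The documents give no effect size, SD, power or participation figure for mu suppression, so there is no stated figure to reproduce.

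Inputs:
- From the Sample Size Calculation: 24 placebo and 48 oxytocin patients, two-sided alpha 0.05 (set there for PANSS and borrowed here).
- Assumed: 80% power; correlation r between screening and Visit 8 mu suppression of 0, 0.5 or 0.7; participation of 100%, 75% or 50%.

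Detectable standardised difference (normal approximation):

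d = (1.96 + 0.84) × √(1/n₁ + 1/n₂) × √(1 − r²)

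- 72 patients: √(1/24 + 1/48) = 0.25, so d = 2.80 × 0.25 = 0.70 at r = 0. At r = 0.7, 0.70 × √0.51 = 0.50.
- 36 patients: √(1/12 + 1/24) = 0.354, so d = 0.99 at r = 0. At r = 0.7, 0.99 × √0.51 = 0.71.

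The noncentral t calculation gives slightly larger values:

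| EEG participants (oxytocin/placebo) | r = 0 | r = 0.5 | r = 0.7 |
|---|---|---|---|
| 72 (48/24) | 0.71 | 0.62 | 0.51 |
| 54 (36/18) | 0.82 | 0.71 | 0.59 |
| 36 (24/12) | 1.02 | 0.88 | 0.73 |

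For a true d of 0.5 with all 72, power is 51%, 62% and 79% for the three values of r.

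Approximate 95% confidence half-width, 1.96 × √(1/n₁ + 1/n₂) × √(1 − r²):
- 72 patients: 1.96 × 0.25 = 0.49 SD at r = 0; 0.49 × √0.51 = 0.35 SD at r = 0.7.
- 36 patients: 1.96 × 0.354 = 0.69 SD at r = 0; 0.69 × √0.51 = 0.49 SD at r = 0.7.

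These figures are before losses. The paradigm requires at least 2 minutes of clean EEG per condition. If each condition has one video of 60 to 80 seconds shown twice (an assumption), the raw recording is 120 to 160 seconds, which leaves little room for artefact rejection.

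**The case against.** A reader might infer that the sponsor intends to claim improvement from the change across the challenge dose, and might calculate how often repeat viewing alone would produce a significant result. The documents do not support that reading. No pre/post test is specified; the single-dose response appears only as a correlate of symptoms. Any false-positive rate would belong to a test the plan does not contain, with a shift the documents do not supply.

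Nor is the challenge wholly without protection. Mu suppression is a log ratio to the moving-ball condition, and non-biological and scrambled displays are included, so general drift in arousal or fatigue largely cancels. This reduces the problem without removing it: a change specific to repeated viewing of biological motion would still look like a drug effect. The protocol's own footnote on cognitive testing relies on the parallel-group design to separate improvement from practice effects; the EEG analysis is given no such control.

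It can also be said that Visit 8 addresses a different question. Section 7 draws on the effect of intranasal dosing on motion perception, the timing of the Visit 8 EEG relative to the last dose is not given, and early terminations make exposure variable. This stands, and it limits interpretation: a null Visit 8 result would not rule out an acute effect. But the objective is not restricted to acute dosing, and this is the only EEG recorded under randomised treatment.

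Finally, this is one secondary objective in an optional sub-study of a pilot, and precision may be poor. That also stands, and it favours reporting an estimate with its interval rather than omitting the comparison. The Missing Data paragraph refers to a further Statistical Analysis Plan, but for the mixed model, sensitivity analyses and assumptions, not for EEG.

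**Conclusion.** The point holds in this form: the objective about improvement has no planned analysis that estimates a drug effect, and the randomised Visit 8/ET EEG is unused. This is more than missing detail, because the listed analyses, carried out exactly, cannot answer the question. The gap is confined to that objective. Aim 7 and the symptom-correlation objective do have analyses, and neither the primary analysis nor safety is affected.

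That the analysis is missing rests on the text alone. The size of what could be learned rests on assumed baseline correlations of 0 to 0.7 and assumed participation: detectable effects of roughly d = 0.5 to 0.7 with all 72 and 0.7 to 1.0 with 36, and worse after dropout and unusable recordings. The comparison would inform on treatment of up to six weeks; it would not establish or refute an acute effect.

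**What to change.** Add one pre-specified secondary analysis to the MU-Suppression paragraph:

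- **Outcome:** Visit 8/ET mu suppression in the biological-motion condition, using one fixed summary of the central sites (for example, the mean of C3, Cz and C4). State the direction, since stronger suppression gives a more negative log ratio.
- **Model:** ANCOVA of pooled oxytocin against placebo, as randomised, among EEG participants, adjusted for mu suppression at the first (pre-challenge) screening EEG. That recording is the suitable covariate because everyone receives the challenge.
- **Reporting:** the adjusted difference with a 95% confidence interval and the number with usable EEG per arm, interpreted as the effect of up to six weeks of treatment and not as an acute effect.
- **Labelling:** describe any change across the challenge dose as uncontrolled and descriptive.

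Fix the sites and condition before unblinding. The challenge dose is given as 24 IU in a schedule footnote but as 24 or 48 IU in the Visit 1 description; these passages must be reconciled so that the descriptive result refers to a defined exposure.

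The cost is one extra analysis on data already scheduled for collection, with no new visit or procedure. The drawback is limited precision, so the interval may be wide.
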